Appendix 1.2 In-App Surveys

Morning Assessments	MidDay	Evening Assessments	
	Assessments		
Stage 1- First assessment			
Post-Concussion Symptom Scale (Modified for App and hereon called Initial Symptom Survey) "How are you feeling this morning? Are	Global: "How are you doing today?" question. If response is "Bad" present symptom survey.	Cognitive Scale: "Please rate 1-5 what you've been doing today" 6- None- No reading, homework, text messaging or screen time (T.V., cell phone), can talk on phone	
you experiencing" 1. A headache: Y/N? 2. Nausea: Y/N? 3. Balance Problems: Y/N? 4. Dizziness: Y/N? 5. Fatigue: Y/N? 6. Drowsiness: Y/N? 7. Sensitivity to light: Y/N? 8. Sensitivity to noise: Y/N? 9. Irritability: Y/N? 10. Sadness: Y/N? 11. Nervousness: Y/N? 12. Feeling more emotional: Y/N?	"Please select what cognitive activities you have been doing today" 1. Socialize with friends 2. Talk on the phone 3. Text friends 4. Watch a short video/T.V. 5. Rest in bed 6. Light Reading 7. Other	 7- Minimal- 15 minutes of screen time or schoolwork 2x daily. Socialize with 1-2 friends, no longer than 30 minutes, 8- Moderate- Homework in 15 minutes blocks for a maximum of 45 minutes. Screen time/T. V in 15-minute blocks, for up to an hour daily. 9- High- Complete as much homework as tolerated. 1 test/week or tests with accommodation (i.e. longer time to write), less reading, homework and screen time than normal 10- Full- no restrictions to cognitive activity 	
13. Feeling Slowed down: Y/N? 14. Mentally foggy: Y/N?		"Please select what physical activities you have done today"	

15. Difficulty concentrating: Y/N?	1. Get up and dressed
16. Difficulty remembering: Y/N?	2. Chores/Housework
17. Visual problems: Y/N?	3. Going for a walk outdoors
18. Confusion with directions/tasks:	4. Other
Y/N?	
19. Move in a clumsy manner: Y/N?	"Daily Symptom survey"
20. Answer questions more slowly than	
usual: Y/N?	
21. Neck pain: Y/N?	
22. Trouble sleeping: Y/N?	
"What Stage of the RTS protocol are	
you in? Select: 1, 2, 3, 4, 5"	
"What Stage of the RTA protocol are	
you in? Select: 1, 2, 3, 4, 5"	

Stage Two			
Daily Symptom survey Page 1: Current symptoms - App generates what was reported yesterday - Global "How are you" question Page 2: New Symptoms	"Please select what cognitive activities you have been doing today" 1- School work 2- Computer time 3- Socialize with friends 4- Text/phone friends 5- Watch video or tv 6- Play a video game 7- Play a board game 8- Read a book 9- Puzzles 10- Other	"Please rate 1-5 what you've been doing today" Cognitive Scale "What Stage of the RTS protocol are you in? Sele 1, 2, 3, 4, 5" "What Stage of the RTA protocol are you in? Sele 1, 2, 3, 4, 5" "What physical activities did you do today?" 1. Brisk Walk 2. Swim 3. Stretch/Yoga 4. Play Catch 5. Walk around the mall/grocery store 6. Walk to the bus/car 7. Move around/clean your room 8. Other "Daily Symptom survey"	
Stage Three			
Page 1: Current symptoms - App generates what was reported yesterday	"Please select what cognitive activities you have been doing today" 1. School work	"Please rate 1-5 what you've been doing today" Cognitive Scale "What Stage of the RTS protocol are you in? Select: 1, 2, 3, 4, 5"	

	 Use iPhone Apps i.e. Snapchat Play on the iPad Watch T.V. Watch a YouTube video Watch a movie Play video games Play a board game Read/Re-read a book Listen to music Puzzles Other 	1, 2, 3, 4, 5" "What physical activities did you do today?" 1. Walk 2. Jog 3. Bike 4. Hike 5. Swim 6. Stretch/Yoga 7. Skate 8. Play Catch 9. Passing, shooting drills 10. Dribbling/Stickhandling 11. Other "Daily Symptom survey"
Page 1: Current symptoms - App generates what was reported yesterday - Global "How are you" question Page 2: New Symptoms	"Please select what cognitive activities you have been doing today" 1. School work 2. Test/Quiz 3. Study 4. Socialize with friends 5. Text/phone friends 6. Use iPhone Apps i.e. Snapchat 7. Play on the iPad 8. Watch T.V. 9. Watch a YouTube video 10. Watch a movie 11. Play video games 12. Play a board game 13. Read/Re-read a book 14. Listen to music 15. Puzzles 16. Other	"Please rate 1-5 what you've been doing today" Cognitive Scale "What Stage of the RTS protocol are you in? Select: 1, 2, 3, 4, 5" "What Stage of the RTA protocol are you in? Select: 1, 2, 3, 4, 5" "What physical activities did you do today?" 1. Jog 2. Bike 3. Hike 4. Swim 5. Stretch/Yoga 6. Skate 7. Play Catch 8. Passing, shooting drills 9. Dribbling/Stickhandling 10. Throwing/Passing drills 11. Sports-specific drills 12. Basketball 13. Soccer 14. Football 15. Hockey 16. Rugby 17. Resistance training 18. Track and Field 19. Squash/Tennis 20. Other "Daily Symptom survey"

Daily Symptom survey

Page 1: Current symptoms

- App generates what was reported yesterday
- Global "How are you" question

Page 2: New Symptoms

"Please select what cognitive activities you have been doing today"

- 1. School work
- 2. Test/Quiz
- 3. Study
- 4. Socialize with friends
- 5. Text/phone friends
- 6. Use iPhone Apps i.e. Snapchat
- 7. Play on the iPad
- 8. Watch T.V.
- 9. Watch YouTube videos
- 10. Watch a movie
- 11. Play video games
- 12. Play a board game
- 13. Read/Re-read a book
- 14. Listen to music
- 15. Puzzles
- 16. Other

"Please rate 1-5 what you've been doing today"

Cognitive Scale

"What Stage of the RTS protocol are you in? Select: 1, 2, 3, 4, 5"

"What Stage of the RTA protocol are you in? Select: 1, 2, 3, 4, 5"

"What physical activities did you do today?"

- 1. Run
- 2. Jog
- 3. Bike
- 4. Hike
- 5. Swim
- 6. Stretch/Yoga
- 7. Skate
- 8. Play Catch
- 9. Jumping jacks/Burpees
- 10. Passing, shooting drills
- 11. Dribbling/Stickhandling
- 12. Throwing/Passing drills
- 13. Sports-specific drills
- 14. Basketball
- 15. Soccer
- 16. Football
- 17. Hockey
- 18. Rugby
- 19. Resistance training
- 20. Track and Field
- 21. Squash/Tennis
- 22. Other

"Daily Symptom survey"

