- Complete the (SUS) after they have finished using the App (Appendix 1.5). Participate in a Follow Up interview (Appendix 1.6) which will assess the youth's experience with their recovery using The Back2Play App, ask about any other interventions they had and if they have experienced a repeat injury during the time in the study.
- Delete the App from their phone during this interview and arrange to return (by scheduled pick up or FedEx label sent by The Research Assistant) device(s).
- 3 months following study enrollment, participants will be sent a survey through REDCap about reinjury to complete.

Participants who have been randomized to the usual care group will be asked to:

- Receive the usual course of care given by the hospital, General Practitioner or clinic which may or may not include written guidelines, suggestions or resources
- Complete the initial post-concussive symptom survey with The Research Assistant.
- Complete symptom surveys and daily surveys about cognitive and physical activities as well as self-rating of participants' own cognitive level of activity and stage of concussion recovery every 24 hours emailed by REDCap until 2 days following symptom resolution.
- Participate in a Zoom visit 2 days after symptom resolution or after 3 months of
 participation for those who do not achieve symptom resolution. Participants will
 be asked questions regarding their knowledge of and ability to follow the Usual
 Care guidelines they received and about any other interventions they may have
 received. This Zoom visit will be recorded and saved to a secure, password
 encrypted study computer.
- 3 months following study enrollment, participants will be asked to complete a survey about reinjury.

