8. DESIGN

Phase 3 of this study has both quantitative and qualitative components. The aims of the qualitative components of the study are to determine if participants liked using The App, and if their experiences of using it helped their recovery from concussion. In addition, qualitative data will be used to review any improvement suggestions to The App before commercialization. Using both qualitative and quantitative research methods we will explore

the usability of The Back2Play App components under consideration for the final version of the App to be commercialized.

Primary Research Outcomes

To assess:

- Risk for repeat head injuries within three months of study completion (3-6 months after injury)
- Duration of symptoms: Time to symptom resolution from date of injury

Secondary Research Outcomes

To assess:

- 1) The frequency of symptoms using PCSS.
- 2) Time to return to activity and time to progress through the 6 stages of RTA
- 3) Perceptions of the platform by parents and youth.
- 4) Accuracy of the algorithm embedded in the background of The App classifying the participant's stage of recovery

Measures

Symptoms

Concussion symptoms will be assessed on The Back2Play App for those randomized to The App group and via REDCap for those randomized to Usual Care. A modified version of the PCSS (consisting of 22 symptoms) will be completed by youth in both groups. The Likert scale was modified to detect the presence of symptoms rather than symptom severity. Symptom data will be collected 3x/day for participants using The Back2Play App and every 24 hours for participants in the Usual Care group.

Cognitive Activity

Cognitive activity will be assessed using a modified version of the scale developed by Brown et al. Participants in both groups will be asked to complete this scale once per day through REDCAP which will appear as follows:

"Please rate 1-5 what you've been doing today"

- 1- None- No reading, homework, text messaging or screen time (T.V., cell phone), can talk on phone
- 2- Minimal- 15 minutes of screen time or schoolwork 2x daily. Socialize with 1-2 friends, no longer than 30 minutes,
- 3- Moderate- Homework in 15 minutes blocks for a maximum of 45 minutes. Screen time/T. V in 15-minute blocks, for up to an hour daily.
- 4- High- Complete as much homework as tolerated. 1 test/week or tests with accommodation (i.e. longer time to write), less reading, homework and screen time than normal
- 5- Full- no restrictions to cognitive activity

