- 16. Participants will be recommended to slow down if their number of symptoms increases by 2
 - o If the participant reports >=2 symptoms are reported worse at all 3 surveys (3x in one day), they will receive the message "Slow down! Take a rest".
- 17. Participants will be provided positive feedback if their number of symptoms increases by 2
 - o If the participant reported >=2 Symptoms logged Better, they will receive the message "Symptoms got better, Great job!"

Activity Recommendations

- 18. Participants will be recommended to reduce their activity if they exceed the following cut points:
 - RTA Stage 1: 5 mins of light activity
 - RTA Stage 2: 60 mins of light activity
 - RTA Stage 3: 120 mins of moderate activity
 - RTA Stage 4: up to 180 mins of vigorous activity
 - RTA Stage 5: Unlimited activity *No Contact
 - RTA Stage 6: Unlimited *Contact
 - o Light activity < 40 steps per minute (Stage 1-2)
 - o Moderate activity 40-93 steps per minute (Stage 3)
 - \circ MVPA \ge 94 steps per minute (Stage 4)
 - o Vigorous (Stage 5-6) doesn't need to be distinguished
 - If the participant exceeds activity recommendations for RTA Stage 1 to 4 and symptoms increase, they will receive the message "Slow down!"

- If the participant exceeds activity recommendations for RTA, they will receive the message "You did a lot of activity today!"
- If the participant meets activity recommendations for RTA Stage 1 to 4, they will receive the message "Great job today!"
- 19. Participants will be cautioned to reduce their activity if their heart rate exceeds 180 bpm
 - o If a child exceeds 180 bpm, the Back2Play App sends a cautionary they will receive the message "You are doing too much!"
 - o If the participant within Stage 1-3 and HR exceeds 180 bpm more than once within an hour, second notification is sent up to 3 notifications/day.

HR, bpm	Excepted	If exceeds, send Notifications
Resting	70-85	100
Peak	180	>180

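### Time to symptom resolution is captured on different platforms and at different frequencies by arm, possibly on different form layouts, and no rule says which record fixes the resolution date

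*Combined protocol and SAP*

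**What the plan says.** Section 8 (Design) lists time to symptom resolution, counted from the date of injury, as a primary outcome and symptom frequency as a secondary one. Under Measures it names one scale: "A modified version of the PCSS (consisting of 22 symptoms) will be completed by youth in both groups". The scale was changed to record presence rather than severity. The same paragraph splits collection by arm: "Concussion symptoms will be assessed on The Back2Play App for those randomized to The App group and via REDCap for those randomized to Usual Care". The App arm is asked three times a day and Usual Care every 24 hours.

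Appendix 1.2 shows the App forms. The first assessment is the full 22-item yes/no list, labelled "Modified for App and hereon called Initial Symptom Survey". From Stage Two the daily symptom survey is laid out differently: a first page for current symptoms ("App generates what was reported yesterday"), with a global question, then a second page for new symptoms. Appendix 1.1 adds notification rules that depend on symptoms being logged as worse or better, for example rule 17: "If the participant reported >=2 Symptoms logged Better".

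For Usual Care, section 7 describes an initial survey with the Research Assistant and then surveys "every 24 hours emailed by REDCap until 2 days following symptom resolution". No REDCap form is reproduced.

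Section 6 states that neither participants nor researchers are blinded. Section 9.5 analyses time to resolution with survival curves and Cox regression. It does not mention the difference in capture, and no section defines symptom resolution.

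**The concern.** A resolution date comes from whatever form the youth fills in. If one arm reviews yesterday's symptoms and the other answers a fresh checklist, or if one arm has three chances a day to report a symptom and the other has one, two youths with the same recovery can be given different dates. The same holds for the daily symptom count.

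The capture method coincides exactly with arm, so no covariate in the Cox model can separate it from treatment. Later data cannot repair it either: in both arms the daily surveys stop 2 days after resolution as recorded. Section 8 also times a reinjury question at 3 months after symptom resolution (section 7 says 3 months after enrolment). On the section 8 wording, a shifted resolution date would move the reinjury window too.

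**Working it through.** **1. What is documented and what is not**

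- Platform: App versus REDCap. Documented as different (section 8).
- Frequency: three times a day versus every 24 hours. Documented as different (sections 7 and 8).
- Named scale: the same modified 22-symptom scale. Documented as the same (section 8).
- Daily layout, App: yesterday's symptoms, then new symptoms. Documented from Stage Two (Appendix 1.2).
- Daily layout, Usual Care: not given.
- Meaning of better or worse on a presence-only scale: not given.
- Definition of resolution (items, threshold, number of clear days, which of the day's surveys): not given. The nearest text, rule 11 in Appendix 1.1, places youth with 2 or fewer symptoms at 24 to 48 hours in a stratum labelled symptom-free, but that rule drives notifications and not the outcome.

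**2. The plan's own figures**

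The sample size in section 3 rests on repeat injury. With the pooled-variance formula n = [1.960·√(2p̄q̄) + 0.842·√(p₁q₁ + p₂q₂)]² / (p₁ − p₂)²:

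- 16% vs 2%: 65 per arm, 130 in total (plan: 128).
- 37% vs 13%: 50 per arm, 100 in total (plan: 100).
- 128 / (1 − 0.20) = 160 (plan: 160).

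These reproduce closely. None depends on time to resolution, so the present point does not change N.

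**3. The 10% effect in days (illustration)**

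Inputs: 59% symptomatic at one month and 14% at three months, from the Alberta study cited in section 2; a 10% decrease in recovery time, from section 3.

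- Exponential through the first point: −ln(0.59)/30 = 0.0176 per day, median 39 days, 10% = 3.9 days.
- Exponential through the second: −ln(0.14)/90 = 0.0218 per day, median 32 days, 10% = 3.2 days.
- The two disagree, so a Weibull curve was fitted through both (30 and 91 days): shape 1.185, scale 51.4, median 37.8 days, 10% = 3.8 days. Multiplying every recovery time by 0.9 on this curve gives a hazard ratio for resolution of (1/0.9)^1.185 = 1.13.

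**4. What a pure measurement shift would do (illustration)**

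Assumptions: the Weibull curve above, no true effect, 160 youths split equally, censoring at 91 days, log-rank test, 1,500 simulations, and the same constant shift for every App-arm youth.

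| Shift in App arm (days) | Apparent HR for resolution | Rejections at two-sided 5% |
|---|---|---|
| 0 | 1.00 | 5% |
| +1 | 0.97 | 5% |
| +2 | 0.96 | 6% |
| +3 | 0.93 | 8% |
| +5 | 0.88 | 11% |
| +7 | 0.84 | 17% |
| −2 | 1.06 | 6% |
| −5 | 1.14 | 11% |

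A shift of −5 days gives about the same hazard ratio as the 10% effect (1.14 against 1.13). A shift of +5 days gives about its reciprocal (1/1.13 = 0.88).

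**5. Frequency alone (illustration)**

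Suppose resolution is the first day on which all m surveys are clear, and after true recovery each survey independently has chance q of a stray yes. The mean extra delay is (1 − p)/p days, with p = (1 − q)^m.

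- q = 0.1: 0.11 days for m = 1, 0.37 for m = 3; difference 0.26.
- q = 0.2: 0.25 and 0.95; difference 0.70.
- q = 0.3: 0.43 and 1.92; difference 1.49.

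Under this rule the App arm looks slower. If resolution were instead the first single clear survey, more frequent asking would give it more chances to look faster. The sign depends on a definition that the plan does not contain.

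**The case against.** The strongest reply is that section 8 assigns one scale to both arms, and silence about REDCap is not evidence of a different form. That stands. A reader might infer that the arms use different instruments; the documents do not say so.

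A reader might also infer that App answers are pre-filled, that a symptom remains until the youth removes it, and that App recovery is therefore recorded late. Appendix 1.2 says only that yesterday's report is generated. It gives no default answer and no removal step, and the two pages together might cover all 22 items. Rules 10 to 13 use symptom counts or disappearance, so the App does register absence in some way. Listing could equally shorten recorded recovery, if symptoms not on the list are not asked about one by one. Any particular lag in days is an assumption.

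Two further replies carry less weight. Both arms have a Zoom visit at which everyone is asked about remaining symptoms (Appendix 1.6). The question is common to both arms, but the visit is timed from recorded resolution and does not date it. And three-times-daily self-monitoring may fairly be called part of the intervention. That is a reason to keep it in the App arm, but not a reason to read the outcome from it.

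Finally, shifts of 1 to 3 days barely move the false-positive rate (5% to 8%). That is correct; the larger worry is a distorted estimate.

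**Conclusion.** The point holds as a gap in specification and ascertainment; a bias has not been demonstrated. A primary outcome that is unblinded and self-reported is collected on different platforms and at different frequencies by arm. The App's printed daily form is not shown as the blank 22-item list of its first assessment, the Usual Care form is not described, and no rule names the record that defines resolution. Whatever artefact arises is inseparable from treatment in the Cox model.

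Its size and direction cannot be obtained from the documents. On curves fitted to the section 2 figures, the effect of interest is 3.2 to 3.9 days, so an artefact of 3 to 5 days either way would be comparable with it and one of a day would matter little. This rests on the fitted curve and on an assumed constant shift. The case for acting is that the remedy is cheap and is available only before data are collected.

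**What to change.** - Give both arms the same 22-item yes/no survey, opened blank, once each evening, in the App or in REDCap. In the App arm, present it before that evening's page listing earlier symptoms.
- Define symptom resolution on that survey: which items count, the threshold, how many consecutive days, and how missed days are handled.
- Derive time to resolution and the symptom counts only from that survey, and say so in section 9.5.
- Keep the App's yesterday's-symptoms page, its better/worse entries and its extra daily surveys for notifications only.
- Reproduce the Usual Care REDCap form beside Appendix 1.2.

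The cost is a survey set-up change, a few sentences of protocol text, and a somewhat longer evening survey in the App arm; the documents give no basis for putting a time on it. The number recruited does not change. The fix removes differences in form and frequency. It does not remove reporting differences due to the lack of blinding or any effect of more frequent self-monitoring on how youth perceive symptoms; these should be acknowledged as limitations.

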The Berlin Consensus 2016 Concussion in Sport Group (CISG)¹, which recently updated The Zurich Consensus³¹, has provided guidelines for return to play for adult athletes which major sport and prevention institutions are readily adopting. These consensus statements were originally designed to provide general recommendations for the management of sport concussion in adults, with the pediatric population being considered in subsequent more recent versions.

While children and youth do present with similar post-concussion symptoms as adults, several investigators and The Berlin Consensus ¹ have noted the need for a more conservative approach for their concussion management due to the unique physiological

make-up among the pediatric patients. ³²⁻³⁴The CanChild Protocols for Concussion Management for children and youth 5-18 years ³⁵⁻³⁷ used in this proposed study were developed with reference to the consensus statements. ¹ The CanChild protocols highlight the need for graduated RTA and RTS management strategies that reflect the pattern of recovery that is unique to each child/youth. Focusing on an individual's unique pattern of recovery may better reflect the complicated course of healing that requires more than a 'one size fits all' set of recommendations.

There are five stages in the CanChild RTS protocol² and six stages in the RTA protocol.² In these protocols, all children/youth are advised that there can be no high-level physical activity or contact sport while symptoms are present. However, 'rest' does not equate to social isolation or sensory deprivation. Daily activities that can be tolerated for each stage of recovery, without symptom exacerbation, are identified in the Activity Suggestions supplement that accompany the protocols, both of which are available on the CanChild website.² Families often find it difficult to gauge the appropriate amount of activity, including cognitive effort, for their child/youth's stage of recovery. The therapeutic goal in managing concussion recovery is to find the individual's level of cognitive and physical exertion that promotes healing which is the focus of our proposed Back2Play App. This graded approach was highlighted in a recent systematic review comparing the difference in concussion management in children/youth versus adults that was part of the CISG 2016 meeting in Berlin.¹ Importantly, this systematic review identified the need for an effective pediatric specific concussion management protocol.³⁸

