7. INTERVENTIONS

Participants randomized to the control group will be provided Usual Care which often is some type of gradual return guidelines the practice (ED, General Practitioner) subscribes to. These are usually provided in a paper format for the patient to take home. Participants in the Usual Care group will complete symptom surveys every 24 hours via REDCap. The Back2Play App requests symptom surveys be done 3 times daily (quickly done on the watch or phone). The Back2play App also asks users to go to the BrainGames App when participants indicate they are ready to progress to the next stage of RTS in the guidelines. In The BrainGames App they can complete 5 neuropsychological tasks that provide feedback about their readiness to progress. These tasks are not available for those in the Usual Care group.

Surveys about cognitive and physical activities engaged in as well as the participants self-rating of cognitive activity level (1-5) and stage of recovery (1-5/6) are done on a daily basis by both groups.

Participants who have been randomized to the App group will be asked to:

- Download The Back2Play App and The B2P BrainGames App on their iPhone and the Apple Watch provided either at the ED or at a scheduled baseline visit (within 2 days of concussion).
- Pair the Apple Watch to their iPhone and wear an Apple Watch for the duration of the study.
- Complete the initial post-concussion symptom survey on the App with the Research Assistant and receive orientation to The Back2Play App.
- Complete 3 symptom surveys per day on The Back2Play App (Morning, Afternoon and Evening) and daily surveys about cognitive and physical activities as well as self-rating of participants' own cognitive level of activity and stage of concussion recovery until 2 days following symptom resolution.
- Complete games on the B2P BrainGames App (i.e. matching games) which are suggested whenever the participant moves up a stage in RTS Protocol.
- Attend a Zoom Follow Up meeting 2 days after symptom resolution or after a maximum of 3 months of using The App. Here, we will ask participants questions about their perceptions of how well The App guided them through their recovery. Did they agree with classifications and notifications, did they understand the guidelines as well as questions about any other interventions they may have received. This Zoom visit will be recorded and saved to a secure, password encrypted study computer.

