
Cognitive and Physical Activities

Engagement in cognitive and physical activities will be measured once per day in those using the App as well as for those in the Usual Care group. The activities surveyed will match those recommended for each stage of RTA/RTS (Appendix 1.2)

Time to Stage

Participants in both groups will report their stage of RTA/RTS. The time from injury to each stage will be used to determine the time to stage and completion of the RTA/RTS guidelines.

Rate of Reinjury

All participants be asked at study completion and 3 months after symptom resolution if they have hit their head again in such a way that they experienced symptom exacerbation or return of symptoms for more than one day, if they moved back a stage in the guidelines for recovery, or if they sought medical care from hitting their head since the initial injury.

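### As printed, the App's return-to-activity item offers Stages 1 to 5 of a six-stage protocol, so Stage 6 and completion of RTA could not be dated if the App follows the appendix

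*Combined protocol and SAP*

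**What the plan says.** Five places in the protocol bear on this point.

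- **Number of stages.** Section 2 (Background) states that there are "six stages in the RTA protocol", against five for return to school (RTS). Rule 18 of Appendix 1.1 separates Stage 5 (unlimited activity, no contact) from the last stage, "RTA Stage 6: Unlimited *Contact".
- **Outcome.** Section 8 lists as a secondary outcome "Time to return to activity and time to progress through the 6 stages of RTA". Return to full activity is also part of the research question.
- **Derivation.** Under Time to Stage, Section 8 says that both groups report their stage, and that "The time from injury to each stage will be used to determine the time to stage and completion of the RTA/RTS guidelines".
- **Range of the rating.** Section 7 says that self-ratings including "stage of recovery (1-5/6) are done on a daily basis by both groups". The natural reading is RTS 1 to 5 and RTA 1 to 6.
- **The item itself.** Appendix 1.2 prints the RTA question as "What Stage of the RTA protocol are you in? Select: 1, 2, 3, 4, 5". The RTS question has the same response list.

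**The concern.** The self-reported stage is the only described source for time to stage and for completion of the guideline. If the item stops at 5, a youth who is back to full contact sport can tick nothing higher than the no-contact stage. The final event of the RTA pathway, which bears most directly on return to full activity, would then have no date in the App arm.

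The comparison between arms is also exposed. The REDCap stage item for Usual Care does not appear in the document. If it offers 1 to 6 while the App offers 1 to 5, only Usual Care youth could complete RTA. If both stop at 5, completion is recorded in neither arm. Either way, a Stage 6 date that was never collected cannot be recovered later from the stage item.

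**Working it through.** The plan states no figure on this point to reproduce, so the check is a comparison of texts followed by a count.

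**Step 1. The RTA response list in each block of Appendix 1.2**

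| Survey block | RTA list as printed |
|---|---|
| Stage 1, first assessment | "you in? Select: 1, 2, 3, 4, 5" |
| Stage Two | "What Stage of the RTA protocol are you in? Sele 1, 2, 3, 4, 5" |
| Stage Three | item wording lost in conversion; the list 1 to 5 survives |
| Fourth block (stage heading not visible) | "What Stage of the RTA protocol are you in? Select: 1, 2, 3, 4, 5" |
| Fifth block (stage heading not visible) | same as the fourth |

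The table is damaged in places. However, each list closes with a quotation mark straight after the 5, including the clipped ones, so a sixth option was not simply cut off in conversion.

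**Step 2. What the outcome needs**

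- Stages defined: 6, giving 6 − 1 = 5 transitions.
- Stages selectable in Appendix 1.2: 5, giving 5 − 1 = 4 datable transitions (1–2, 2–3, 3–4, 4–5).
- Transition lost: 5–6.

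Time in a stage is the date of entry to the next stage minus the date of entry to the current one. Times to Stages 2, 3, 4 and 5, and time spent in Stages 1 to 4, are unaffected. Entry to Stage 6, time spent in Stage 5 and completion of RTA all need the missing report.

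**Step 3. Is there another dated source?**

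The follow-up interview in Appendix 1.6 asks whether the youth is fully back at school and sport, but records neither a stage nor a date. Section 7 places the follow-up visit two days after symptoms resolve, or at 3 months, so it may come before Stage 6. The 3-month survey in Section 7 is about reinjury. No other described source supplies the date.

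**Step 4. Would a sixth option be enough?**

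Section 7 ends daily stage reporting two days after symptom resolution in both arms. Section 2 advises against contact sport while symptoms are present, and rule 18 describes Stage 6 as contact. A youth who follows that advice could report Stage 6 only in a window of about two days. The option is necessary, but on its own it would capture few Stage 6 dates.

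**The case against.** The strongest reply is that this is a drafting conflict, not a fact about the software. Section 7 gives one range, reaching 6, for both groups. Appendix 1.1 refers to RTA Stage 6 in rule 18 and, in the message under rule 2, to RTA Stages 4 to 6. Section 2 calls Appendix 1.2 a summary of the surveys, and the RTS list may simply have been copied to the RTA item. All of this stands. It limits the conclusion to what follows if the appendix was built as printed. It does not remove the point, because Appendix 1.2 is the only place where the item and its options are specified.

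A reader might infer more than the documents support:

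- **That no App participant can have a Stage 6 date.** Section 7 and Appendix 1.1 point the other way, and the programmed item is not shown.
- **That time through the RTA stages cannot be measured at all.** Four of the five transitions remain datable.
- **That using Stage 5 as the end point dates return too early by at least 24 hours, 48 hours or 1 week.** Those figures in rules 11 to 13 are advice messages on stage length, not enforced minimums, and rule 7 anticipates skipped stages.
- **That evaluation of the algorithm is damaged.** Section 1 says that stages were collapsed and that the current model predicts RTA Stages 2 to 5 only, so Stage 6 is already not a separate predicted class.
- **That the comparison is biased against the App.** This needs a REDCap item offering 1 to 6 beside an App item offering 1 to 5. The documents do not show the REDCap item, and Section 7 gives both groups the same range.

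**Conclusion.** The point holds as an internal contradiction with a definite consequence if left alone. Appendix 1.2 lists RTA 1 to 5 in every block, against six stages in Sections 2 and 8 and Appendix 1.1, and a range reaching 6 in Section 7. An App built to the appendix would lose one of five transitions, and with it time spent in Stage 5 and completion of RTA. A difference in end point between arms is possible but conditional on a form that is not shown.

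This affects part of one secondary outcome; neither primary outcome depends on it. It is still worth correcting before data are collected, because the change is cheap and the loss would be permanent. The conclusion assumes that the range in Section 7 means RTS 1 to 5 and RTA 1 to 6, and that no dated source for Stage 6 exists beyond those described.

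**What to change.** 1. Reconcile Appendix 1.2 with Sections 2, 7 and 8 and with rule 18: print the RTA response set as 1 to 6 in every survey block and leave RTS at 1 to 5. Check the built App against the corrected text.
2. Use the identical two stage items in the Usual Care REDCap survey, and show them in the protocol.
3. State in Section 8 which report defines completion of RTA, with the same definition in both arms.
4. Secure a Stage 6 date after daily reporting ends: ask both arms, in the existing 3-month survey, for the date RTA Stage 6 was reached. Alternatively, state that youth not yet at Stage 6 are censored when reporting stops. The added question is the better choice, because reporting stops when symptoms have just resolved and censoring then would be tied to recovery itself.

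The cost is one response option, one survey item and a check of the build. No extra visit or change in sample size is needed.
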